10.3.4 Reporting of SAEs

SAE Reporting to Bayer Pharmacovigilance via Paper Data Collection Tool

- Email transmission of the SAE paper data collection tool is the preferred method to transmit this information to Bayer Pharmacovigilance.
- In rare circumstances and if email transmission is not feasible, notification by telephone is acceptable with a copy of the SAE data collection tool sent by overnight mail or courier service.
- Initial notification via telephone does not replace the need for the investigator to complete and sign the SAE data collection tool within the designated reporting time frames.
- Contacts for SAE reporting:
[contact] or [contact] (Germany)

10.4 Appendix 4: Contraceptive Guidance and Collection of Pregnancy Information

Definitions:

Woman of Childbearing Potential (WOCBP)

A woman is considered fertile following menarche and until becoming post-menopausal unless permanently sterile (see below).

If fertility is unclear (e.g., amenorrhea in adolescents or athletes) and a menstrual cycle cannot be confirmed before first dose of study intervention, additional evaluation should be considered.

Women in the following categories are not considered WOCBP

1. Premenarchal
2. Premenopausal female with 1 of the following:
 - Documented hysterectomy
 - Documented bilateral salpingectomy
 - Documented bilateral oophorectomy

For individuals with permanent infertility due to an alternate medical cause other than the above, (e.g., mullerian agenesis, androgen insensitivity), investigator discretion should be applied to determining study entry.

Note: Documentation can come from the site personnel's: review of the participant's medical records, medical examination, or medical history interview.

3. Postmenopausal female

- A postmenopausal state is defined as no menses for 12 months without an alternative medical cause.
- Females on HRT and whose menopausal status is in doubt will be required to use one of the non-estrogen hormonal highly effective contraception methods if they wish to continue their HRT during the study. Otherwise, they must discontinue HRT to allow confirmation of postmenopausal status before study enrollment.

Contraception Guidance:

Female participants who become pregnant

- The investigator will collect pregnancy information on any female participant who becomes pregnant while participating in this study. The initial information will be recorded on the appropriate form and submitted to the sponsor within 24 hours of learning of a participant's pregnancy.
- The participant will be followed to determine the outcome of the pregnancy. The investigator will collect follow-up information on the participant and the neonate and the information will be forwarded to the sponsor. Generally, follow-up will not be required for longer than 6 to 8 weeks beyond the estimated delivery date. Any termination of pregnancy will be reported, regardless of fetal status (presence or absence of anomalies) or indication for the procedure.
 - While pregnancy itself is not considered to be an AE or SAE, any pregnancy complication or elective termination of a pregnancy for medical reasons will be reported as an AE or SAE.
 - A spontaneous abortion (occurring at <22 weeks gestational age) or still birth (occurring at >22 weeks gestational age) is always considered to be an SAE and will be reported as such.
- Any post-study pregnancy related SAE considered reasonably related to the study intervention by the investigator will be reported to the sponsor as described in Section 8.4.4. While the investigator is not obligated to actively seek this information in former study participants, he or she may learn of an SAE through spontaneous reporting.
- Any female participant who becomes pregnant while participating in the study will be withdrawn from the study.

10.5 Appendix 5: Abbreviations

| | |
|---------|--|
| ADHD | attention deficit hyperactivity disorder |
| AE | adverse event |
| AUC | area under the curve |
| BAY no. | BAY number is the main identifier for compounds within the Bayer HealthCare Organization |
| bid | twice a day |
| BMI | body mass index: weight [kg] / (height [m]) ² |
| CDISC | Clinical Data Interchange Standards Consortium |
| CFR | Code of Federal Regulations |
| CI | confidence interval |
| CIOMS | Council for International Organizations of Medical Sciences |
| cm | centimeter |
| COX | cyclooxygenase |
| CRO | contract research organization |
| CV | coefficient of variation |
| (e)CRF | (electronic) case report form |
| e.g. | exempli gratia (for example) |
| FDA | Food and Drug Administration |
| FSH | follicle stimulating hormone |
| g | grams |
| GCP | good clinical practice |
| HIPAA | Health Insurance Portability and Accountability Act |
| HR | heart rate |
| HRT | hormonal replacement therapy |
| i.e. | id est (that is) |
| IB | investigator's brochure |
| ICF | informed consent form |
| ICH | International Council for Harmonisation |
| IEC | independent ethics committee |
| IMP | investigational medicinal product |
| IRB | institutional review board |
| kg | kilogram |
| (c)L | (centi)liter |
| MedDRA | medical dictionary for regulatory activities |
| mm | millimeter |
| NSAID | nonsteroidal anti-inflammatory drug |
| OTC | over the counter |
| POM | pain on movement |
| QA | quality assurance |
| RNR | randomization number |

| | |
|-------|---|
| SoA | schedule of events |
| SAE | serious adverse event |
| SAP | statistical analysis plan |
| SNR | screening number |
| SoA | Schedule of Activities |
| SOP | standard operating procedure |
| SSRI | selective serotonin uptake inhibitors |
| SUSAR | suspected unexpected serious adverse reaction |
| TEAE | treatment emergent adverse event |
| UI | unique identifier (drug formula) |
| USA | United States of America |
| VAS | visual analog scale |
| WOCBP | woman of childbearing potential |

11. References

SAS	Statistical Analysis System
SD	Standard deviation
SoA	Schedule of Assessments
TFL	Tables/Figures/Listings
Vi	Visit i, i=1, 2, ..., 7
VAS	Visual Analogue Scale
vs.	versus
WHO	World Health Organization

	Trial Substance:	BAY H6689	Study No.:	21559
	Short Title:	Acute Soft Tissue of the Lower Extremities	Sponsor:	BAYER HEALTHCARE LLC.

1 INTRODUCTION

General information on methods and procedures for the statistical evaluation are described in the Clinical Study Protocol (CSP), Final Version/Amendment 3, dated 09 November 2021. The Statistical Analysis Plan (SAP) presented here outlines the evaluations to be performed in the final statistical analysis, including details with respect to endpoint derivation, applied statistical methods, and presentation of the results.

This SAP refers to the latest version of the amended Study Protocol (Version 4.0). The SAP will be finalized after the Data Blind Review Meeting (DBRM) and contains a comprehensive and detailed elaboration of the statistical methodology section of the protocol.

2 DESIGN OF THE CLINICAL TRIAL

The study is a Phase II (proof-of-concept), randomized (2:2:1), double-blind, multi-center, active- and placebo-controlled, parallel group clinical trial to compare the efficacy and safety of 10 % Naproxen Gel versus a 2.32 % diclofenac diethylamine gel and placebo in the treatment of acute soft tissue injuries of the lower extremities, conducted in Germany.

Approximately 100 participants will be screened to achieve 75 randomized to study intervention for an estimated total of 30 evaluable participants per each active cohort and 15 participants in the placebo cohort.

The duration of each patient's participation in the study will be 6 consecutive days (from randomization (V1) to Final Visit (V11)).

3 TIME SCHEDULE

The study consists of 11 visits: randomization visit (Visit 1, 0 h, Day 1), and post-baseline visits Visit 2 (12 h after first treatment, Day 2), Visit 3 (24 h after first treatment, Day 2), Visit 4 (36 h after first treatment, Day 3), Visit 5 (48 h after first treatment, Day 3), Visit 6 (60 h after first treatment, Day 4) and Visit 7 (72 h after first treatment, Day 4), Visit 8 (84 h after first treatment, Day 5), Visit 9 (96 h after first treatment, Day 5) Visit 10 (108 h after first treatment, Day 6), and final Visit 11 (120 h after first treatment, Day 6). A detailed schedule of Assessments is presented in the CSP, Final Amended Version 4.0 approved 09 November 2021, Chapter 1.3, p. 13.

4 TRIAL OBJECTIVES

4.1 Primary objective

To assess the effectiveness of a naproxen topical gel 10% diclofenac diethylamine 2.32%, and placebo for relieving tenderness to pressure in subjects with acute soft tissue injuries of the lower extremities.

4.2 Secondary objectives

The secondary objectives are:

- To assess the safety of a naproxen gel 10% diclofenac diethylamine gel 2.32% and placebo during a 5-day treatment period;
- To assess adverse events.

	Trial Substance:	BAY H6689	Study No.:	21559
	Short Title:	Acute Soft Tissue of the Lower Extremities	Sponsor:	BAYER HEALTHCARE LLC.

4.3 Other objectives

To evaluate pain on movement and tenderness to pressure over various time periods and at individual time points.

5 SUBJECTS ASSESSMENTS

5.1 Efficacy variables

5.1.1 Primary efficacy variable

The primary efficacy outcome is Tenderness (Algometry) over the initial 72 hours (Algometry AUC₀₋₇₂).

5.1.2 Other efficacy variables

Other efficacy variables are:

- VAS POM over the initial 12-hours (VAS AUC₀₋₁₂), 24-hours (VAS AUC₀₋₂₄), 36-hours (VAS AUC₀₋₃₆), 48-hours (VAS AUC₀₋₄₈), 60-hours (VAS AUC₀₋₆₀), 72-hours (VAS AUC₀₋₇₂), and 120 hours (VAS AUC₀₋₁₂₀);
- Change of VAS POM at hours 12, 24, 36, 48, 60, 72 and 120 from baseline (BL);
- VAS POM over the initial 72-hours (VAS AUC₀₋₇₂) in the subgroups “sprain/strain” and “contusion”.
- Change of Algometric Tenderness (N/cm²) at hours 12, 24, 36, 48, 60, 72, and 120 from baseline;
- Algometric Tenderness (N/cm²) over the initial 12-hours (N/cm² AUC₀₋₁₂), 24- hours (N/cm² AUC₀₋₂₄), 36-hours (N/cm² AUC₀₋₃₆), 48-hours (N/cm² AUC₀₋₄₈) 60-hours (N/cm² AUC₀₋₆₀) and 120 hours (N/cm² AUC₀₋₁₂₀);
- Ratio of algometry injured/contralateral sites over 72 hours and 120 hours (N/cm² Ratio AUC₀₋₇₂ and N/cm² Ratio AUC₀₋₁₂₀);
- Algometry over the initial 72-hours (N/cm² AUC₀₋₇₂) in the subgroups “sprain/strain” and “contusion”.
- Percent of subjects with no (zero) VAS POM at 120 hours;
- Global assessment of treatment efficacy at 24 hours, 48 hours, 72 hours, and 120 hours by patients using a 5-point scale (0=none, 1=poor, 2=fair, 3=good, 4=excellent);
- Global assessment of treatment efficacy at 72 hours in the subgroups “sprain/strain” and “contusion”.
- Change of VAS PAR at hours 12, 24, 36, 48, 60, 72 and 120 from baseline (BL).

5.2 Safety variables

Secondary efficacy variables are:

- Safety (percentage of subjects with at least one TEAE);
- Incidence of adverse events.

The following parameters are recorded to assess the safety of the study drug:

- Adverse events (AEs).
AEs will be documented at Visit 1 to Visit 11.
- Vital signs and body temperature.

	Trial Substance:	BAY H6689	Study No.:	21559
	Short Title:	Acute Soft Tissue of the Lower Extremities	Sponsor:	BAYER HEALTHCARE LLC.

Pulse rate (bpm) and blood pressure (BP_s, BP_d (mmHg) as well as body temperature will be documented at the Baseline Visit (Visit 1), Visit 7, and Final Visit (Visit 11)).

- General physical examination.

Physical examination will be performed at Visit 1 (randomization visit), Visit 2, Visit 4, Visit 6, Visit 8, and Visit 10, as well as when judged necessary by the Investigator.

A general physical examination will be performed at Visit 1 and include the injured extremity and assessments of the Dermatological, Cardiovascular, Respiratory, Gastrointestinal and Neurological systems.

A limited physical examination of the injured extremity will be performed at Visits 2, 4, 6, 8 and 10. Any issues will be described as adverse event.

Examination will include general condition, dermatologic, eyes, ears, nose, throat, neck, thyroid, heart, respiratory system, abdomen, kidneys, skeletal system, extremities, lymphatic system, CNS, neurological conditions and other (to be specified).

- Height and body weight.

Height in centimeters (cm, without shoes) and body weight (kg, in indoor clothing, but without shoes) will be measured at Visit 1. The corresponding Body Mass Index (BMI) will be calculated.

- Pregnancy and assessments of fertility.

Female participants of child-bearing potential will undergo urine pregnancy testing at Visit 1 (prior to first dose) and Visit 10 (prior to last dose).

- Global tolerability

Global tolerability will be assessed by the investigators and the patients according to the following numerical scale at Visits 3, 5, 7, and 11, respectively:

- 0: poor
- 1: fair
- 2: good
- 3: very good
- 4: excellent.

- Sensory questions

During the final visit of the study (Visit 11), patients will be asked two sensory questions related to the IMP they received.

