5.1 Inclusion Criteria

Participants are eligible to be included in the study only if all of the following criteria apply:

Age

1. Participant must be 18 to 60 years of age inclusive, at the time of signing the informed consent.

Type of Participant and Disease Characteristics

2. Participants with a primary diagnosis of acute sports-related acute soft tissue injuries of the lower extremities that do not require hospitalization and that occurred within 3 hours of enrollment.
3. Participants with a baseline algometric measurement values on the injured site of $\leq 50\%$ of the respective value at the contralateral site.
4. Participants with a baseline (POM) of ≥ 50 mm on a visual analog scale (VAS) (0–100 mm).
5. Participant's absolute sensitivity to tenderness on the contralateral site is at least 2.5 N/cm² as measured by algometry.
6. Participant's size of trauma is between 25 and 150 cm².

Informed Consent

7. Capable of giving signed informed consent as described in Section 10.1.4 which includes compliance with the requirements and restrictions listed in the informed consent form (ICF) and in this protocol.

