8.3.1 Physical Examinations

A general physical examination will include the injured extremity and assessments of the Dermatological, Cardiovascular, Respiratory, Gastrointestinal and Neurological systems at Screening (Visit 1). Height and weight will also be measured and recorded.

A limited physical examination of the injured extremity will be performed at Visits 2, 4, 6, 8 and 10. Changes related to the physical exam will be documented on the source documents and case report form.

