9.4.5 Safety Analysis

Safety will be measured by adverse events (AEs) and vital signs. Only descriptive analyses will be conducted on the Safety Population. No imputation will be made for missing safety data. Quantitative data for safety variables will be described by summary statistics for the original data as well as for the differences to baseline when it is appropriate. Frequency tables will be provided for qualitative data. No statistical test will be planned regarding the safety analyses.

Only treatment-emergent AEs will be included in the summary analysis, i.e., AEs that begin or worsen after the first application of Investigational Medicinal Product (IMP). The number and percent of subjects who experience any event and the number of events overall, by System Organ Class, and by Preferred Term will be displayed by treatment group. Tables will also be produced by severity and relationship to IMP. Seriousness, severity, relationship to IMP duration, and outcome will also be listed.

Listings of individual data will be presented.

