- Signs, symptoms, or the clinical sequelae of a suspected overdose of either study intervention or a concomitant medication. Overdose per se will not be reported as an AE/SAE unless it is an intentional overdose taken with possible suicidal/self-harming intent. Such overdoses should be reported regardless of sequelae.
- The signs, symptoms, and/or clinical sequelae resulting from lack of efficacy will be reported as AE or SAE if they fulfill the definition of an AE or SAE.

Events NOT Meeting the AE Definition

- Any clinically significant abnormal laboratory findings or other abnormal safety assessments which are associated with the underlying disease, unless judged by the investigator to be more severe than expected for the participant's condition.
- The disease/disorder being studied or expected progression, signs, or symptoms of the disease/disorder being studied, unless more severe than expected for the participant's condition.
- Medical or surgical procedure (e.g., endoscopy, appendectomy): the condition that leads to the procedure is the AE.
- Situations in which an untoward medical occurrence did not occur (social and/or convenience admission to a hospital).
- Anticipated day-to-day fluctuations of pre-existing disease(s) or condition(s) present or detected at the start of the study that do not worsen.

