14.5 Safety

The assessment of safety will be based mainly on the frequency of AEs that are treatment-emergent in the Safety Population. Formal statistical tests will not be conducted for differences in safety parameters between treatment groups. Only descriptive analyses will be conducted.

The incidence of all treatment-emergent AEs will be after grouping by body system and preferred term. For each preferred term and summarized over each body system overall, the table will present the number of patients in each treatment group in whom the event occurred and the rate (%) of occurrence. The incidence of all suspected-drug-related AEs will be tabulated similarly. The incidence of all treatment-emergent AEs will also be tabulated by severity

	Trial Substance:	BAY H6689	Study No.:	21559
	Short Title:	Acute Soft Tissue of the Lower Extremities	Sponsor:	BAYER HEALTHCARE LLC.

categories and relationship to the IMP. Seriousness, severity, relationship to IMP duration and outcome will also be listed.

Safety will also be summarized with respect to vital signs as mean levels by visit and change from baseline. Abnormal observations on physical exams will be listed.

The ordinal outcome (global assessment of tolerability) will be analyzed by the Cochran-Mantel-Haenszel test of general association, stratified by center and also by subgroup (strain/sprain, contusion).

Furthermore, the ordinal outcome (sensory questions) will also be analyzed by the Cochran-Mantel-Haenszel test of general association, stratified by center and also by subgroup (strain/sprain, contusion).

Listings of individual data will be presented.

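### SAP 5.2 makes any finding on the injured limb an adverse event, which conflicts with protocol 10.3.1 and, if followed, would inflate the TEAE percentage

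*SAP*

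**What the plan says.** **SAP 5.2 (Safety variables).** After the general examination at Visit 1, "A limited physical examination of the injured extremity will be performed at Visits 2, 4, 6, 8 and 10". The next sentence is "Any issues will be described as adverse event". It has no exception and does not refer to the protocol's adverse event definition.

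**Protocol 10.3.1 (Definition of AE).** The list of events that do not meet the definition includes "The disease/disorder being studied or expected progression, signs, or symptoms of the disease/disorder being studied, unless more severe than expected" for the participant's condition.

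**Protocol 8.3.1 (Physical Examinations).** "Changes related to the physical exam will be documented on the source documents and case report form". Nothing there makes such a change an adverse event automatically.

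**SAP 14.5 (Safety).** "Abnormal observations on physical exams will be listed". SAP 14.5.2 repeats this.

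**The endpoint.** Protocol section 3 and SAP 5.2 both name the percentage of subjects with at least one TEAE as a secondary variable. Protocol 9.4.5 defines a TEAE by onset or worsening after the first application. The SAP uses the term but does not define it.

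**The concern.** The five limited examinations look only at a limb whose injury was recent at entry: protocol 5.1 requires an injury "that occurred within 3 hours of enrollment". At least 50 of the 75 randomised subjects are to have contusions (protocol 4.1). Signs of such an injury can still be developing after the first application. The treatment-emergent rule does not remove them, because they begin or worsen after dosing. The protocol's exclusion of expected signs is what keeps them out of the adverse event data, and the SAP sentence omits it.

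At stake is the meaning of the TEAE percentage in a study intended to guide further development (protocol 2.1). The main known risks of the naproxen gel are application site reactions such as erythema and irritation (protocol 2.3.1). These arise on the same skin that is examined for injury signs, so a single overall percentage would mix the two.

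**Working it through.** **Step 1: compare the texts.** Take a bruise on the injured limb, first seen at Visit 2 and no worse than the investigator expected.

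| Rule | Result |
|---|---|
| SAP 5.2 | Adverse event, because every issue is one |
| Protocol 10.3.1 | Not an adverse event: an expected sign, not more severe than expected |
| Protocol 8.3.1 | Recorded in source documents and CRF |
| Protocol 9.4.5 | If it is called an adverse event, it is treatment-emergent, because it began after the first application |
| SAP 14.5 | Listed if abnormal; silent on adverse event status |

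The first two rows cannot both be followed. The fourth shows that the SAP rule would carry the finding into the endpoint. A baseline injury that stays unchanged is kept out by the same treatment-emergent rule.

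**Step 2: illustrate the size.** Neither document states a TEAE rate or a rate of injury findings, so there is no planned figure to reproduce. All rates below are assumptions.

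*Chance that a subject acquires at least one such event.* Let v be the chance that one examination leads to an expected sign being called an issue. Over five independent examinations the chance of at least one is 1 − (1 − v)^5:

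- v = 2%: 1 − 0.98^5 = 9.6%
- v = 5%: 1 − 0.95^5 = 22.6%
- v = 10%: 1 − 0.90^5 = 41.0%
- v = 20%: 1 − 0.80^5 = 67.2%

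Findings in one subject are likely to be positively correlated, which lowers these figures. With complete dependence the chance falls to v itself.

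*Effect on the reported percentage.* Let p be the true TEAE rate under protocol 10.3.1 and q the chance that a subject has an expected injury sign recorded as an adverse event. Take p and q as independent and q as equal in all arms. The reported rate is 1 − (1 − p)(1 − q), and the difference between arms becomes (p_active − p_placebo)(1 − q). With p = 10% on active gel and 5% on placebo:

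| q | Active | Placebo | Difference |
|---|---|---|---|
| 0% | 10.0% | 5.0% | 5.0 points |
| 10% | 1 − 0.90 × 0.90 = 19.0% | 1 − 0.95 × 0.90 = 14.5% | 4.5 points |
| 30% | 1 − 0.90 × 0.70 = 37.0% | 1 − 0.95 × 0.70 = 33.5% | 3.5 points |
| 50% | 1 − 0.90 × 0.50 = 55.0% | 1 − 0.95 × 0.50 = 52.5% | 2.5 points |

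**Step 3: scale.** With 30 subjects per active arm and 15 on placebo (SAP section 2), one subject is 1/30 = 3.3 points or 1/15 = 6.7 points. The loss of contrast in the table, at most 2.5 points, is less than one placebo subject. The rise in level is larger: at q = 30% it is 27.0 points on active gel and 28.5 on placebo.

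**The case against.** The strongest objection is that SAP 5.2 is not where adverse events are decided. Protocol 8.4 makes the investigator responsible for detecting and recording them under the section 10.3 definitions. SAP 5.2 recaps assessments, and no SAP rule converts examination records into adverse events. The SAP is also to be finalised only after the blind review meeting, when the site data exist. This largely stands: the endpoint is affected only if the sentence reaches CRF completion guidance, which is not among the documents, or shapes queries (SAP 11) or blind review (SAP 12). It does not remove the conflict between the two texts.

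Four stronger readings are tempting, and the documents do not support them.

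- **The endpoint would count the injury itself.** The treatment-emergent rule excludes an injury unchanged since before the first application. Only expected signs that begin or worsen afterwards are at issue.
- **The SAP contradicts its own analysis section.** SAP 14.5 says abnormal examination findings will be listed, not that they will only be listed. Listing a finding is compatible with also recording an adverse event, and so is the CRF documentation in protocol 8.3.1. The conflict is between SAP 5.2 and protocol 10.3.1.
- **Gel reactions would be hidden.** TEAEs are also tabulated by preferred term, severity and relationship to IMP, with a separate table of suspected drug-related events (SAP 14.5). A skin reaction would still appear there. What is diluted is the overall percentage.
- **An irritating gel would look safer than placebo.** This needs injury findings to differ between arms. With assumed injury findings of 45% on gel and 60% on placebo, and gel reactions of 10% and 2%, the rates are 1 − 0.90 × 0.55 = 50.5% and 1 − 0.98 × 0.40 = 60.8%. The reversal is arithmetically possible, but nothing in the documents supports those inputs.

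**Conclusion.** Wrong as written, minor. The SAP states a rule for examination findings that the protocol's adverse event definition excludes. Whether any TEAE count would change depends on the sentence being applied in data collection or review, which the documents do not show.

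If it is applied, the TEAE percentage rises in every arm by an unknown amount. The reduction in differences between arms also assumes a similar background of injury findings in each. Adverse events are summarised descriptively without tests (protocol 9.4.5, SAP 14.5), so no error rate, power or sample size is affected. The harm is confined to the interpretation of one overall descriptive percentage.

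**What to change.** 1. Replace the sentence in SAP 5.2 with: *Findings at the injured extremity are recorded as adverse events only if the investigator judges that they meet protocol 10.3.1; expected signs or progression of the injury, unless more severe than expected, are documented and listed only.* The test should not be whether a finding is new, because a bruise first appearing on Day 2 is new and still expected.
2. Repeat the protocol 9.4.5 TEAE definition in the SAP.
3. Check that the CRF completion guidance agrees with protocol 10.3.1.
4. Query to the investigator, before unblinding, any recorded adverse event that looks inconsistent with protocol 10.3.1. Analysts should not remove such events when deriving the TEAE flag, because that would override the investigator's judgement.

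The cost is a small text change plus whatever queries arise, using the query and blind review steps already planned in SAP 11 and 12. No endpoint, test or sample size changes.
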